## 1. Objectives

### 1.1. Purpose, specific aims, or objectives:

The purpose of this proposal is to test the efficacy of yoga as a mind and body intervention to decrease stress, anxiety, and depression in parents of critically ill neonates hospitalized in the Seattle Children's and University of Washington neonatal intensive care units (NICUs). Specific aims include developing a randomized controlled pilot study to elucidate the optimal research strategy with which to implement mind and body interventions for parents of NICU patients. We will ultimately use these data to plan a multicenter Randomized Controlled Trial (RCT) to evaluate the short and long-term effects of yoga practice on NICU parents, the parent-child interaction, and child outcomes.

### 1.2. Hypotheses to be tested:

We hypothesize that a combined program of breath work, physical practice and meditation will decrease parental stress, anxiety, and depression in the NICU, improve parent-child bonding, and through this, child, and family outcomes.

## 2. Background

### 2.1. Relevant prior experience and gaps in current knowledge:

Preterm infants are often critically ill and require prolonged hospitalization in neonatal intensive care units (NICUs). The care of these infants is often regionalized, so that they can get the specialized treatment needed in centers with expertise in delivering this care. An unintended consequence of regionalization is the physical and emotional isolation parents experience when they stay with their hospitalized child far from family, friends, and work. As a result of these stressors, loss of parental control, autonomy, and concern for their child's wellbeing, nearly half of NICU mothers develop anxiety, depression, or posttraumatic stress disorder, and this may persist for years.

Helping parents to cope with the birth and hospitalization of a preterm infant is critical for the parents' health and wellbeing, as well as for the optimal development of their child, as parental anxiety and depression may affect parent-child bonding and result in altered child development. The practice of yoga, which encompasses physical postures (asana), but also includes breathing techniques (pranayama), and meditation (dhyana), has proven benefits in many areas of medicine and wellness including stress management, mental and emotional health and promoting sleep. Given the positive effects on both physical and emotional health, these mind and body techniques are promising as a therapeutic modality by which parental stress, anxiety and depression could be reduced.

There are gaps in our knowledge as previous studies of yoga have not occurred in hospital settings and have not included subjects in an acute state of distress such as parents of critically ill hospitalized neonates. Furthermore, in the current COVID-19 environment it is important to explore ways to make yoga interventions available to families by remote access, and to test whether this approach is successful.

Faculty advisors of this project have extensive prior experience with design and completion of multicenter trials involving newborn infants in NICUs across the United States. To allow us to evaluate the use of yoga as a means for helping parents cope with hospitalization of their newborn infants, we have enlisted a team of yoga practitioners including a registered prenatal and postnatal yoga teacher ([name]), UW NICU RN, yoga teacher and NICU parent advocate ([name]). Faculty advisor [name] is also a certified Yoga and

Meditation teacher and will provide guidance in the design of the yoga intervention for NICU parents.

## 2.2. Relevant preliminary data:

This is the continuation of a prior project: Yoga in the NICU Pilot Study see 2.4.

Surveys were completed by both NICU parents (n=31) and hospital stakeholders (n=140) to assess the feasibility and desirability of a yoga intervention for NICU parents. Preliminary data for Aim 1 suggest that NICU parents struggle primarily with stress and anxiety compared with depression. Parents with an infant hospitalized at UW NICU or SCH NICU primarily cope with the admission through social support (e.g., talking with friends and family), though mindfulness and meditation activities are considered important as well. A small percentage of hospital stakeholders surveyed had concerns about the safety (22%) and liability (14%) of a yoga intervention for parents, however most stakeholders had few concerns.

We were pleased to learn through our survey data that hospital stakeholders strongly view an intervention of yoga for NICU parents to increase parent satisfaction and confidence. Overall, there was overwhelming support from both parents and stakeholders in both institutions for a yoga intervention for parents of NICU babies.

## 2.3. Scientific or scholarly background:

See 2.1

## 2.4. Prior approvals:

Yoga in the NICU Pilot Study approved (exempt status) by UW IRB ID# STUDY00010722

## 3. Study Endpoints

### 3.1. Primary and secondary endpoints:

Goal would be to enroll parents of NICU inpatients from UWMC and SCH into the study on a rolling basis for 4-6 months or until we have enrolled a total of 20 parents to the intervention and 20 parents to the control groups spanning both institutions. The intervention lasts for a duration of 6 weeks.

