- **Meditation (Dhyana)** = guided meditation

The goal of this project is to conduct a pilot study to both allow optimization of engagement for a future definitive study, and to obtain empirical estimates of effect sizes and variability within the target study population.

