### SELF-REPORT SURVEYS:

*Yoga in the NICU Introduction Survey:* demographic survey completed on a smart device at the time of enrollment. This survey (see supplemental materials) will include basic demographic data including age, ethnic background, race, education level, employment status, assessment of household food insecurity (measure of SES), assessment of prior mental health treatment (in the past 12 months before delivery of premature baby), assessment of yoga practice prior to and during pregnancy (for either birth parent or participating partner). We will also collect a personal email address where subsequent study surveys will be sent directly from REDCap.

To further assess parental stress, anxiety and depression, participants in both arms of the study will complete the following surveys (see supplemental materials)

1. *Depression, Anxiety, Stress Scale (DASS21)*: to assess baseline participant depression, anxiety, and stress with these three self-report scales. Each of the three scales contains 7 items divided into subscales with similar content (depression, anxiety, and stress). Scores for depression, anxiety and stress are calculated by summing the scores for relevant items.
  - Two-times: at enrollment and conclusion of study
2. *Parental Stress Scale: Neonatal Intensive Care Unit (PSS:NICU)* a 26-item self-report scale designed to measure the degree of stress experienced by parents during hospitalization related to alterations in their parental role, the appearance and behavior of their child, and sights and sound of the unit.
  - Three times: at study start, midpoint (3 weeks) and at the conclusion of the study
3. *Postpartum Bonding Questionnaire (PBQ)* a 19-item self-report scale evaluating two factors involved in parent-infant bonding.
  - One time: at conclusion of the study
4. *Course Completion Survey* filled out by all participants at the conclusion of the study. There will be specific questions in this survey directed through branching logic to parents in the intervention group relating to safety and adverse events as well as parent opinions about the yoga intervention.

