5.4. Data to be collected, including long-term follow-up data:

**Infant Demographics:** gestational age (weeks), birth weight (g), postnatal age at enrollment and discharge (days)

**Infant characteristics:** Apgar score (5 min), inborn (n), multiparous birth (n), primary and secondary diagnoses (BPD, NEC, PDA, RDS, GI/GU, cardiac, other), IVH (grade), mechanical ventilation at study start (y/n), length of assisted ventilation (days), length of stay (days), any breastfeeding at discharge (y/n)

**Parent Demographics:** age, ethnicity, race, highest level of education, employment status, marital status, other children at home, mode of delivery (vaginal/c-section), experience with yoga before and during pregnancy

**Parent characteristics:** Edinburgh Postnatal Depression Scale scores (located in the infant EPIC chart (UWMC) or the maternal EPIC chart (SCH), or administered by study coordinator at time of enrollment)

**Parent study data:** YIN Introduction Survey, EPDS (if not administered by unit social worker) DASS21, PSS:NICU, PBQ, post-study questionnaire, participation in yoga intervention (tracked on rise website): sessions started (n), duration of participation (min)

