## 9.2. Exclusion criteria for each subject population:

- Expected length of stay of NICU inpatient < 6 weeks
- Parent only speaks or reads in a language other than English or Spanish
- Parent plans to relinquish child
- Child or parents are too unstable as assessed by the Attending Physician

9.2.1. Justification if subjects who use a language other than English or subjects with a parent/legally authorized representative (LAR) who uses a language other than English, will be excluded from the research:

The goal of this pilot study is to generate data to support a parent mindfulness intervention of yoga, breath work, and meditation to reduce stress, depression, and anxiety of parents with infants hospitalized in the NICU. Based on the small sample of parent participants, the inclusion of multiple languages to this study population may confound our research or render appropriate analysis of the data impractical. Further limitations of including a population that uses a language other than English or Spanish include lack of appropriate validated instruments, surveys, or assessments published in other languages to determine parental stress and parent-child bonding for NICU parents.

To improve equity within this project the PI ([name]) is submitting this modification of the current IRB to include Spanish speaking parents. The results of this pilot study will be used to generate a universally accessible parent mindfulness intervention that is inclusive of all ethnicities and languages with the goal to be inclusive of every parent in the NICU regardless of their language of care.

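### The endpoint section (3.1) holds a recruitment goal and no outcome is designated primary, yet the protocol sets an efficacy test and claims power 0.80

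*Protocol*

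**What the plan says.** Section 3.1 is the protocol's endpoint section. Its text is a recruitment target, "Goal would be to enroll parents of NICU inpatients from UWMC and SCH into the study on a rolling basis for 4-6 months" or until 20 parents per arm are enrolled, followed by the 6-week duration of the intervention. Section 3.2, on safety endpoints, is marked not applicable.

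The purpose is stated in two ways. Section 1.1 says the proposal is to "test the efficacy of yoga as a mind and body intervention to decrease stress, anxiety, and depression in parents", and then gives as a specific aim "developing a randomized controlled pilot study to elucidate the optimal research strategy". Section 5.1 gives only the pilot purpose: to optimise engagement and "to obtain empirical estimates of effect sizes and variability within the target study population".

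Section 5.2 lists the instruments without ranking them:

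- DASS21, with separate depression, anxiety and stress scores: "Two-times: at enrollment and conclusion of study".
- PSS:NICU, "designed to measure the degree of stress experienced by parents during hospitalization": at start, 3 weeks and conclusion.
- PBQ: once, at conclusion.

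Section 5.4 adds yoga sessions started and minutes of participation. Section 5.2 does settle whose data count: each family designates a primary participant before randomization, and the second parent is exploratory.

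Section 10.4 expects stress and anxiety to fall by 20-30% and derives 16 parents per group for power 0.80 at alpha 0.05, raised to 20 for attrition. It names no scale, score, cut-off, SD, time point or test.

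**The concern.** An efficacy test and a power statement each need one defined outcome, and the section meant to supply it supplies something else. Footnote 3 of the protocol's own template explains that an endpoint is something measured to show whether the intervention helps. A recruitment target is not that. The choice of primary outcome is a protocol decision, not a detail for an analysis plan.

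Two things are at stake. First, the power in 10.4 cannot be attached to any comparison, so the size of the trial is not justified for its stated purpose. Second, the outcome could be chosen after data have been seen. Under 16.1 the investigator looks at self-report data from both arms every week, as a safety review. Under 25.2.4 interim results are presented at the midpoint. Nothing suggests that a data-driven choice is intended, but the document does not rule one out.

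**Working it through.** **1. Is an outcome designated anywhere?** Sections 1.1, 1.2, 3.1, 5.1, 5.2, 5.4, 10.4 and 14.1 were compared. The word primary is applied to a participant, a diagnosis and the investigator's role, never to an outcome. Section 1.2 lists stress, anxiety, depression, bonding, and child and family outcomes without order.

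**2. Can the 16 per group in 10.4 be reproduced?** Inputs from 10.4: baseline about 50% (literature, anxiety) or about 60% (own survey, anxiety and stress); decrease 20-30%; alpha 0.05; power 0.80. Whether the decrease is absolute or relative, and whether the test is one- or two-sided, is not stated.

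Read as proportions, with p̄ = (p1+p2)/2 and the two-sided pooled normal test:

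- n per group = [1.96·√(2p̄(1−p̄)) + 0.8416·√(p1(1−p1)+p2(1−p2))]² / (p1−p2)²
- power = Φ{[√n·(p1−p2) − 1.96·√(2p̄(1−p̄))] / √(p1(1−p1)+p2(1−p2))}

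Most favourable case, 50% to 20%: n = (1.322 + 0.539)²/0.09 = 38.5, so 39. Power at n = 16 is Φ[(1.200 − 1.322)/0.640] = Φ(−0.19) = 0.42.

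| Change | Reading | Power, n=16 | n per group for 0.80 |
|---|---|---|---|
| 50% to 40% | relative 20% | 0.08 | 388 |
| 50% to 35% | relative 30% | 0.13 | 170 |
| 50% to 30% | absolute 20 | 0.21 | 93 |
| 50% to 20% | absolute 30 | 0.42 | 39 |
| 60% to 48% | relative 20% | 0.10 | 270 |
| 60% to 42% | relative 30% | 0.17 | 120 |
| 60% to 40% | absolute 20 | 0.20 | 97 |
| 60% to 30% | absolute 30 | 0.40 | 42 |

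With all 20 per group, power runs from 0.09 to 0.51. A one-sided test does not rescue the figure: the best case needs 31 per group and has power 0.56 at 16. For 16 per group to suffice two-sided, the rate must fall by about 43 points from 50% or 46 points from 60%. A one-sample, one-sided test of 60% against 30% does give 16, but that is not a comparison of two arms. The step from 16 to 20 is consistent with 20% attrition: 16/(1−0.20) = 20.

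Read as a mean score, a two-sample t-test with power 0.80 detects 1.02 SD with 16 per group and 0.91 SD with 20. With no mean or SD in the protocol, a 20-30% decrease cannot be converted to SD units.

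**3. What could an open choice cost?** Assumptions not in the protocol: each score is tested at 0.05, any success counts, and scores are equally correlated at 0 to 0.7. With independence, two scores (for example DASS21 stress and anxiety) give 1 − 0.95² = 9.75%, and three (for example the three DASS21 scores) give 1 − 0.95³ = 14.3%. At correlation 0.7 these become 8.4% and 10.9%.

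**4. Does timing constrain the choice?** PSS:NICU measures stress during hospitalization. Section 19.1 starts the intervention 10-14 days after admission, so the 3-week assessment falls at day 31-35 (+21) and the 6-week one at day 52-56 (+42). Section 9.2 excludes "Expected length of stay of NICU inpatient < 6 weeks", so the shortest expected stay is 42 days if counted from admission.

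**The case against.** The strongest reply is that this is a pilot. The word recurs throughout, 5.1 sets estimation as the goal, and 1.1 says the data will be used to plan a multicenter trial. An unranked outcome does less harm here than in a definitive trial. That is right about degree, but the pilot goal designates no endpoint either, and it cannot stand beside an efficacy test and a power of 0.80.

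Other objections stand in part:

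- The n = 16 problem is separable from the missing endpoint, and the shortfall in power follows only if 10.4 means proportions. If it means a mean score, the claim cannot be checked rather than being contradicted. Both readings still need an outcome before 10.4 can be repaired.
- Section 16.1 concerns referral of individual parents, and 25.2.4 does not say that outcomes will be shown by arm. With enrolment from August 2021, few 6-week assessments would exist in October. The selection risk is possible, not shown.
- The false-positive figures are illustrative, since no section says any success would count.
- Section 5.2 already fixes the analysed parent, and DASS21 and PBQ each have only one later assessment. What remains open is the scale and score, plus the time point for PSS:NICU.
- The 42 days are a floor on expected stay, and the protocol does not say from when it is counted. Many infants may still be in hospital at day 52-56.

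**Conclusion.** The concern holds. The endpoint section contains no endpoint, no other section supplies one, and the efficacy test in 1.1 and the power claim in 10.4 therefore refer to no defined comparison. On the only percentages 10.4 gives, 16 per group has about 8-42% two-sided power, not 80%. On a mean-score reading the trial needs a difference of about 1 SD, which the protocol does not support with any SD. Leaving the choice open could raise the false-positive chance from 5% to about 8-10% for two scores or 11-14% for three, under the assumptions in step 3.

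This should be corrected. It concerns a small, minimal-risk pilot and can be put right in the text, but it decides whether any efficacy statement from the trial can be interpreted.

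**What to change.** Replace the text of 3.1 with one of two options; the choice is the sponsor's.

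**(a) Keep the efficacy aim.** Name one primary outcome by scale, score, time point and analysed person. An example is DASS21 stress at the end of the 6 weeks in the designated primary parent, compared between arms with adjustment for the enrolment value. List the other scores as secondary, with estimates and confidence intervals and no efficacy claim. Restate 10.4 for that outcome. With 16 per group the detectable difference is 1.02 SD unadjusted. With adjustment it is 1.02·√(1−r²): 0.98, 0.89 or 0.73 SD for an assumed enrolment-to-end correlation r of 0.3, 0.5 or 0.7. If PSS:NICU is preferred, choose a time point at which the infant is still expected to be in hospital. The 3-week one meets this but comes only halfway through the intervention.

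**(b) Let the pilot goal govern.** Name two primary endpoints: engagement in the yoga arm (sessions started, minutes), and estimation of the between-arm difference and its SD. Remove the efficacy-test wording from 1.1 and the power claim from 10.4, and justify the size by precision for each:

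- Between-arm difference, 95% CI half-width t·√(2/n): 0.64 SD with 20 per arm, 0.72 SD with 16.
- Mean sessions or minutes in one arm, t/√n: 0.47 SD with 20, 0.53 SD with 16.

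Neither option needs new data collection. Option (a) commits the sponsor to one headline outcome and a less favourable 10.4. Option (b) gives up an efficacy claim from this trial.

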### 3.2. Primary or secondary safety endpoints:

N/A

## 4. Drugs, Devices and Biologics

### 4.1. Manufacturer and name of all drugs, devices and biologics:

N/A

### 4.2. Description and purpose of all drugs, devices and biologics:

N/A

### 4.3. Regulatory status of all drugs, devices and biologics:

N/A

4.3.1. Drugs or Biologics:

- IND Exempt. Explain: N/A
- IND.

4.3.2. Devices:

- IDE Exempt. Explain: N/A
- Abbreviated IDE / Non-Significant Risk. Explain: N/A
- IDE / Significant Risk.

4.4. Plans to store, handle, and administer any study drugs, devices and biologics so they will be used only on subjects and be used only by authorized investigators:

N/A

## 5. Procedures Involved

### 5.1. Study design:

This will be a randomized controlled pilot study to elucidate the optimal research strategy with which to implement mind and body interventions for **parents** of NICU patients, at 2 sites (University of Washington NICU and Seattle Children's Hospital NICU) comparing: 1) control group 2) yoga intervention (i.e: breathing exercises + meditation +postures).

Parents will be enrolled in the study after day 10 of infant admission to NICU and begin participation by day 14 of NICU admission (see Recruitment methods section 19).

The non-birth parent will be invited to participate in this study and may participate without the birth parent. If both parents are participating the partner would be randomized to the same group (control or intervention) see randomization section 5.2. In the circumstance that the birth parent declines participation and non-birth parent consents to participation, we will still obtain consent from parents to access infant medical records, however we will not obtain birth parent EPDS scale (see section 5.2)

If an infant is transferred from UWMC to SCH as part of their clinical care, a parent enrolled initially at UWMC may continue participation in this study while infant is admitted at SCH.

**Control group:** Parents will experience usual care including all available parental support as practiced in the specific site NICU. We will utilize a 'waitlist' control model for this project, whereby the parents randomized to control group will have unlimited access to the online platform hosting the yoga intervention following the completion of the study period.

**Intervention group:** In addition to usual care, the parents randomized to the intervention group will be provided a yoga mat and participate in 30-min online led yoga sessions done at least twice weekly at the parent's pace using a secure, virtual platform (website). There will be 6 total yoga classes (one introduced per week for a 6 week period). Each yoga session will be divided into three components, which will vary in duration based on a curriculum designed *specifically* with the post-partum state of mothers in mind:

- **Yoga postures (Asana)** = low impact gentle postures meant to be done individually
- **Breathing techniques (Pranayama)** = deliberate modifications of breath such as rapid

- diaphragmatic breathing, slow/deep breathing, alternate nostril breathing, breath holding
- **Meditation (Dhyana)** = guided meditation

The goal of this project is to conduct a pilot study to both allow optimization of engagement for a future definitive study, and to obtain empirical estimates of effect sizes and variability within the target study population.

## 5.2. Research procedures:

**Screening:** see section 19

**Randomization:** The parent(s) who consent to participate in the study will be randomized using a 2x2 computerized block randomization ([www.sealedenvelope.com/simple-randomiser/v1/lists](http://www.sealedenvelope.com/simple-randomiser/v1/lists)). Participants will be stratified by NICU into two groups A) usual care B) yoga intervention. At the time of consent, the study coordinator will be **blinded to the randomization**, and the parent will be presented with a sealed envelope that identifies group A (control) and group B (intervention).

When both parents from the same family are eligible and interested in study participation, both will be consented and then randomized to the same group and followed separately with outcome surveys. Since parental outcomes are likely correlated. Prior to randomization we will ask parents to designate one parent as the primary study participant. Outcomes of the parent designated as the secondary study participant will be included in exploratory analyses that appropriately accounts for potentially correlated outcomes.

**Intervention Group:** Parents will receive an information sheet (see 'Welcome Packet YOGA GROUP' in "other attachments" ) explaining the practice of yoga, meditation and breathing exercises, FAQs about the study including how to access an electronic tablet while in the unit (if parent is unable to supply their own device), instructions on how to access study website and Zoom. Parents will also sign the study consent form and HIPAA authorization, receive a personal yoga mat, ear-pods (if needed), and details regarding compensation for the study (see 23.1). Participants have the opportunity to keep the ear-pods and yoga mat at the conclusion of the study. Parents in the intervention group will receive usual care for parent support offered in site NICU and be enrolled in a 6-week virtual yoga curriculum (see description in 5.1). They will also be asked to periodically fill out questionnaires throughout the study.

**Control Group:** Parents will sign the study consent and HIPAA forms. Information will be provided regarding the waitlist control model (see 5.1), and details about the compensation for the study (see 23.1). Parents in the control group will receive usual care for parent support offered in site NICU. They will also be asked to periodically via email to fill out identical questionnaires as the intervention group throughout the 6-week study period.

In general, a participating non-birth parent may skip self-report items that are considered not applicable, however there should be very few items that cannot be answered by either parent.

